**IIS PROTOCOL SYNOPSIS**

**Protocol Title:** Fycompa titration intervals and effects on retention rates

**Principal Investigator Name:** [name]

**Principal Investigator Contact Information:** [name]  
[contact] [contact]  
[[contact]](mailto:[contact])

**Institution Name(s):** Banner University Medicine Neuroscience Institute

**Sub-Investigator Name, if applicable:** [name]  
[name]

**Do you plan on using other Institutions or centers to conduct study?**  YES  NO

**If yes, please list name(s) and address(es):** N/A

**Rationale:** With its novel mechanism of AMPA receptor blockade, Fycompa is efficacious for seizure reduction in both partial onset seizures and generalized tonic-clonic seizures. As only a few of antiepileptic medications have this capability, it is important to elucidate the ideal methods of avoiding complications and improving retention rates.

Recent studies find real-world rates currently range from 44-89% (Trinka et al 2016). Personal clinical experience has revealed difficulty in maintaining patients on Fycompa due to adverse effects. However, certain studies find correlations between slower titration schedules and lower side effect percentages (Trinka et al 2016, Lawthom et al, 2014).

We therefore propose to test whether a slower initial upward titration (2mg increase every 3 weeks) improves 1-year retention rates as compared to those of a more typical titration every 2 weeks. As any retention rate may be affected by adverse effects and/or seizure frequency, these will be followed as secondary endpoints.

**Study Design:** A total of 60 patients with a confirmed diagnosis of either partial onset or primary generalized epilepsy will be recruited into the trial. 30 patients will initiate Fycompa at a dose of 2 mg/day and titrate upward every 2 weeks to a target dose of 6 mg/day. Patients in this group will be designated Group A. The remaining 30 patients will also begin Fycompa at a dose of 2 mg/day but will titrate upwards every 3 weeks to a target dose of 6 mg/day and will be designated Group B. Initial study visits will occur every two weeks for the first 2 months in order to assess for titration related adverse effects. Long term evaluation of retention rates will be calculated at 3, 6, 9 and 12 months after enrollment.

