**Secondary:**

1. To compare the adverse effects reported in patients up-titrating Fycompa at a slower titration rate (Group B) to those titrating at a more conventional rate (Group A).
2. To evaluate the short term and long term efficacy of perampanel between the two treatment groups.

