## IIS PROTOCOL SYNOPSIS

- Other Therapy:** Concomitant antiepileptic and medical treatment will be allowed as deemed necessary by the Principle investigator and/or sub-investigators. .
- Efficacy Measures:** Patient diaries containing seizure types and frequencies along with adverse effects experienced will be maintained. Seizure diaries will be reviewed in Epilepsy Clinic during study visits occurring at the following intervals: weeks 0, 2, 4, 6, 8 then months 3, 6, 9, and 12. Data point collation at study visits will include:
1. Fycompa dose taken and duration at this dose
  2. Adverse effects experienced
  3. Alterations to Fycompa dose once in maintenance phase.
  4. Interim seizure types and number of each
  5. Interim changes in other medication during maintenance phase.
- Safety Measures:** Adverse effects and seizure frequency will be assessed at each clinic visit along with vital sign measurements and brief neurological exams. Dosage adjustments of the Fycompa and other concomitant medications will be done at the discretion of the Investigator during the maintenance phase.
- Correlative Science:** Data collected will be based on the patient's seizure/adverse effect diary as well as patient/caregiver reports at each study visit.
- Statistical Analysis:** The study will target a total size of 60 patients (30 per group). This sample size will allow for a power of 0.85 to determine significant difference of 30% retention in group A and 70% retention in group B.
- Primary endpoint will be Fycompa retention rate at the end of 1 year with Kaplan-Meier survival curves created for both groups. Log rank testing will be done to determine significant difference ( $p < 0.05$ ). Cox proportional hazard test will be done to quantify the odds of retention in each arm.
- Secondary endpoint analysis will be done to tabulated side effects experienced in each group and the percentages of patients reporting the effects. Seizure frequency per 28 days during initial titration and final maintenance will be calculated for each group. Comparison within groups will be made by ANOVA.
- Data Collection:** Data will be collected at each study visit through patient interview and the use of a seizure/adverse effect diary.

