**Study Drug Regimens:**

Group A will have Fycompa 2mg qD for 2 weeks, then 4mg qD for 2 weeks, then 6mg qD for at least 2 weeks. Further adjustments upward or downward in the maintenance phase will be allowed as per Investigator's discretion. We anticipate 15 will continue at 6mg, 8 will decrease to 4mg, and 7 will increase to 8mg during the next 46 weeks of maintenance.

Group B will have Fycompa 2mg qD for 3 weeks, then 4mg qD for 3 weeks, then 6mg qD for at least 3 weeks. Further adjustments upward or downward in the maintenance phase will be allowed as per the Investigator's discretion. We anticipate 15 will continue at 6mg, 8 will decrease to 4mg, and 7 will increase to 8mg for the remaining 40 weeks of maintenance.

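### Secondary objective 2 asks for efficacy between the randomised groups, but the only seizure-frequency test planned is within groups, over two periods that are not defined

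*Combined protocol and SAP*

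**What the plan says.** Objectives, Secondary, item 2: "To evaluate the short term and long term efficacy of perampanel between the two treatment groups". The Rationale gives seizure frequency the status of a secondary endpoint: "As any retention rate may be affected by adverse effects and/or seizure frequency, these will be followed as secondary endpoints".

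IIS Protocol Synopsis, Statistical Analysis, on that endpoint: "Seizure frequency per 28 days during initial titration and final maintenance will be calculated for each group". The next sentence is the only one that names a test for it: "Comparison within groups will be made by ANOVA". The log-rank test and the Cox model in the same section are attached to one-year retention.

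Neither period is given dates in the analysis text. The nearest information stands under Study Drug Regimens, which reads for the first arm: "Group A will have Fycompa 2mg qD for 2 weeks, then 4mg qD for 2 weeks, then 6mg qD for at least 2 weeks", and for the second arm: "Group B will have Fycompa 2mg qD for 3 weeks, then 4mg qD for 3 weeks, then 6mg qD for at least 3 weeks". The same section anticipates 46 further weeks of maintenance in Group A and 40 in Group B.

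Subjects and Centers states that patients are randomly assigned, 30 to each group.

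**The concern.** The objective and the analysis ask different questions. The objective is a contrast between A and B, which randomisation supports. The named test, read as written, contrasts two periods inside one arm. That contrast mixes any drug effect with time, dose and regression to the mean, and it yields two p values, neither of which concerns the difference between titration schedules.

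The practical risk lies in interpretation. With two separate p values and no planned contrast, a report can easily slide from a significant change in one arm only to a claim that the schedules differ in efficacy. A direct comparison is what the objective needs, and it requires periods that mean the same thing in both arms.

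**Working it through.** **The plan's own figure.** The only power stated is 0.85, for retention ("significant difference of 30% retention in group A and 70% retention in group B"). It reproduces with the Freedman log-rank formula, two-sided 0.05:
- Hazard ratio = ln(0.7)/ln(0.3) = 0.296; expected events = 30 × 0.7 + 30 × 0.3 = 30.
- Power = Φ(√30 × (1 − 0.296)/(1 + 0.296) − 1.960) = Φ(1.01) = 0.845.

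This figure is sound and has no bearing on seizure frequency, for which the documents give no effect size, SD or power. Everything below therefore uses assumed values, shown as ranges.

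**Text against text.** Objective: between groups. Summary: one value per group and period. Test: within groups. Between-group test, estimate or interval for seizure frequency: none anywhere in the document.

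**Illustration under the literal reading.** With two periods, a within-arm ANOVA is a paired test. Take n = 30 in each arm (best case, nobody missing), two-sided 0.05, and the same true change d in both arms. Power p comes from the noncentral t distribution, and the chance that exactly one arm is significant is 2p(1 − p).

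| d (SD of change) | p | 2p(1 − p) |
|---|---|---|
| 0.2 | 0.185 | 0.30 |
| 0.3 | 0.355 | 0.46 |
| 0.4 | 0.563 | 0.49 |
| 0.5 | 0.754 | 0.37 |
| 0.6 | 0.888 | 0.20 |
| 0.8 | 0.988 | 0.02 |

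In simulation at d = 0.3 to 0.6, a direct between-group t test on the same data rejected in about 5% of trials, its nominal level.

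**The periods.** Group A: 2 + 2 + 2 = at least 6 weeks of titration; 52 − 46 = 6. Group B: 3 + 3 + 3 = at least 9 weeks; 52 − 40 = 12. The 52-week year is an assumption. A length of 12 weeks satisfies a minimum of 9, so the figures are compatible, but the period is longer in B than in A and its end is not fixed.

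**Separate caveat: who has late data.** At the planned retention, 30 × 0.30 = 9 patients in A and 30 × 0.70 = 21 in B would still be on drug at one year. I assume that only they have final-maintenance data, that the true improvement is equal (0.5 SD), and that retention is governed by a latent score correlated r with improvement. Over 40,000 simulated trials per setting, a between-group t test on retained patients gives:

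| r | falsely significant | mean shift favouring A (SD) |
|---|---|---|
| 0 | 0.05 | 0 |
| 0.3 | 0.08 | 0.19 |
| 0.5 | 0.14 | 0.32 |
| 0.7 | 0.26 | 0.45 |

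**Precision of the proposed comparison.** Detectable at 80% power with 30 per arm: (1.960 + 0.842) × √(2/30) = 0.72 SD (0.74 with the t distribution). With 9 versus 21: 2.802 × √(1/9 + 1/21) = 1.12 SD. For a negative binomial rate ratio over weeks 0 to 8 (two 28-day periods, full diaries), SE = √(2(1/μ + k)/30), with μ the mean count and k the dispersion:
- 8 seizures per 28 days, k = 0.5: μ = 16, SE 0.194, 95% CI around a ratio of 1 of 0.68 to 1.46.
- 2 seizures per 28 days, k = 2: μ = 4, SE 0.387, 95% CI 0.47 to 2.14.

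**The case against.** The best defence is that *within* is a slip. ANOVA is often used to compare groups, and the preceding sentence produces a value for each group. That may well be so. In that case the illustration of discordant p values does not apply. What remains is a wrong word, no stated contrast or interval, and undefined periods.

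Four stronger readings are tempting, and the documents do not support them.
- A reader might infer that 0.20 to 0.49 is the plan's error rate. It is not. The plan nowhere says that significance in one arm alone will be taken as a group difference, and the figures depend on assumed effect sizes and the paired reading.
- A reader might infer that Group B's titration lengths, 9 and 12 weeks, contradict each other. They do not, because 9 is a minimum and 12 rests on a 52-week year. The 40 weeks also stand in a sentence anticipating dose use, not in a definition of an analysis period.
- A reader might attribute the selection problem to the ANOVA sentence. It comes from dropout and would affect any test of late seizure frequency, including the one proposed here. Nothing in the documents supports a high correlation: the Rationale blames adverse effects for the difficulty in keeping patients on drug, though it also allows a role for seizure frequency. At r = 0.1 and 0.2 the false-positive rate is only 0.055 and 0.061.
- A reader might infer that the trial plans no comparison of the randomised groups. It does, for retention.

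It is also fair to say that this is an unpowered secondary endpoint in a 60-patient synopsis and that a correct analysis will be imprecise. That limits the consequence. It does not justify a test of a different question.

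**Conclusion.** The concern holds in this form: for seizure frequency, the analysis as written cannot answer secondary objective 2, and correcting the one word would still leave the contrast, interval and periods unspecified. This rests on the text alone and needs no assumption. It should be fixed, but it does not touch the primary retention analysis or the sample size.

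The numbers only illustrate. Discordance between arms of 0.20 to 0.49 requires the paired reading, 30 patients per arm with data, and an equal true change of 0.2 to 0.6 SD; by 0.8 SD it falls to 0.02. The false-positive rate of about 0.05 to 0.26 for a retained-only comparison requires exactly 9 and 21 patients with data and r between 0 and 0.7. It is a caveat on the long-term result, separate from the defect in the sentence.

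**What to change.** Replace the ANOVA sentence with a comparison of 28-day seizure frequency between groups, B versus A as randomised, with a 95% CI for each of the two periods. Use a method suited to skewed counts, for example a negative binomial rate ratio with log diary days as offset; a rank-based test is an alternative. Keep within-group changes as description only.

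Define the two windows so that they cover the same time from randomisation in both arms and fall on existing visits. One option is weeks 0 to 8 for the short term and the last visit interval, months 9 to 12, for the long term. Weeks 0 to 8 end two weeks after Group A's minimum titration period (8 − 6) and one week before Group B's (9 − 8), so this restates what the plan calls titration and should be written as a definition.

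Label the long-term comparison as an on-drug estimate open to selection by who stays on drug, and report the number contributing in each arm. The early window has less dropout but is not immune.

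The cost is some further analysis work, a restated definition of the two periods, and acceptance of an imprecise estimate (about 0.72 SD detectable at 80% power with 30 per arm). The diaries and visits already exist, so no extra visits are needed.

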**Study Drug Regimens:**

Group A will have Fycompa 2mg qD for 2 weeks, then 4mg qD for 2 weeks, then 6mg qD for at least 2 weeks. Further adjustments upward or downward in the maintenance phase will be allowed as per Investigator's discretion. We anticipate 15 will continue at 6mg, 8 will decrease to 4mg, and 7 will increase to 8mg during the next 46 weeks of maintenance.

Group B will have Fycompa 2mg qD for 3 weeks, then 4mg qD for 3 weeks, then 6mg qD for at least 3 weeks. Further adjustments upward or downward in the maintenance phase will be allowed as per the Investigator's discretion. We anticipate 15 will continue at 6mg, 8 will decrease to 4mg, and 7 will increase to 8mg for the remaining 40 weeks of maintenance.

**Study Drug Requested Per Patient:**

TOTAL: 2mg tablets = 11,550  
4mg tablets = 24,794

Are Clinical/Drug Supplies Requested? (check only 1 box):  'YES'  'NO'

|   |                       |
|---|-----------------------|
| Total study drug amount in units (tablets, capsules, vials, etc.): |                       |
| Total Active Drug  | 36,344 tablets |
| Amount of Pure Substance (if applicable)                           |                       |

## IIS PROTOCOL SYNOPSIS

|   |   |
|---|---|
| Estimated Study Start Date:                                      | February 1, 2017  |
| Estimated Length of Enrollment:                                  | 2 years   |
| Description of Site Enrollment Capabilities:                     | The Banner University Medicine Neuroscience Institute, Epilepsy Center includes 3 full-time epileptologists, each with weekly outpatient clinics for epilepsy patients. It also employs a full-time study coordinator.  |
| Estimated Study Duration:  | 24 months from study initiation to data analysis and paper completion, allowing for a 12 month enrollment period.   |
| Potential written outcomes of this study (check all that apply): |  Final Study Report  Submit for Presentation at scientific conference
 Submit for Publication  Submit Abstract/Poster at scientific conference |
| Publication Plan (if applicable):                                | Epilepsia, submission in August 2020.   |

